8.3.4.2. Local Reactions

During the reactogenicity e-diary reporting period, participants will be asked to assess redness, swelling, and pain at the injection site and to record the symptoms in the reactogenicity e-diary. In Substudy A, local reactions will be assessed at the injection site on the right arm.

If a local reaction persists beyond the end of the reactogenicity e-diary period following vaccination, the participant will be requested to report that information. The investigator will enter this additional information in the CRF.

Participants will be provided with a measuring device. Redness and swelling will be measured and recorded in measuring device units (range: 1 to 21) and then categorized during analysis as absent, mild, moderate, or severe based on the grading scale in Table 1. Measuring device units can be converted to centimeters according to the following formula: 1 measuring device unit = 0.5 cm. Pain at the injection site will be assessed by the participant as absent, mild, moderate, or severe according to the grading scale in Table 1.

If a Grade 3 local reaction is reported in the reactogenicity e-diary, a telephone contact should occur to ascertain further details and determine whether a site visit is clinically indicated. Only an investigator or medically qualified person is able to classify a participant's local reaction as Grade 4. If a participant experiences a confirmed Grade 4 local reaction, the investigator must immediately notify the sponsor.

Table 1. Local Reaction Grading Scale

	Mild (Grade 1)	Moderate (Grade 2)	Severe (Grade 3)	Potentially Life-Threatening (Grade 4)
Pain at the injection site	Does not interfere with activity	Interferes with activity	Prevents daily activity	Emergency room visit or hospitalization for severe pain
Redness	>2.0 cm to 5.0 cm (5 to 10 measuring device units)	>5.0 cm to 10.0 cm (11 to 20 measuring device units)	>10 cm (\geq 21 measuring device units)	Necrosis or exfoliative dermatitis
Swelling	>2.0 cm to 5.0 cm (5 to 10 measuring device units)	>5.0 cm to 10.0 cm (11 to 20 measuring device units)	>10 cm (\geq 21 measuring device units)	Necrosis

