8.3.4.3. Systemic Events

During the reactogenicity e-diary reporting period, participants will be asked to assess vomiting, diarrhea, headache, fatigue, chills, new or worsened muscle pain, and new or worsened joint pain and to record the symptoms in the reactogenicity e-diary. The symptoms will be assessed by the participant as absent, mild, moderate, or severe according to the grading scale in [Table 2](#).

If a systemic event persists beyond the end of the reactogenicity e-diary period following vaccination, the participant will be requested to report that information. The investigator will enter this additional information in the CRF.

If a Grade 3 systemic event is reported in the reactogenicity e-diary, a telephone contact should occur to ascertain further details and determine whether a site visit is clinically indicated. Only an investigator or medically qualified person is able to classify a participant's systemic event as Grade 4. If a participant experiences a confirmed Grade 4 systemic event, the investigator must immediately notify the sponsor and, if it is determined

to be related to the administration of the study intervention, further vaccinations will be discontinued in that participant.

Table 2. Systemic Event Grading Scale

	Mild (Grade 1)	Moderate (Grade 2)	Severe (Grade 3)	Potentially Life-Threatening (Grade 4)
Vomiting	1-2 times in 24 hours	>2 times in 24 hours	Requires IV hydration	Emergency room visit or hospitalization for hypotensive shock
Diarrhea	2 to 3 loose stools in 24 hours	4 to 5 loose stools in 24 hours	6 or more loose stools in 24 hours	Emergency room visit or hospitalization for severe diarrhea
Headache	Does not interfere with activity	Some interference with activity	Prevents daily routine activity	Emergency room visit or hospitalization for severe headache
Fatigue/tiredness	Does not interfere with activity	Some interference with activity	Prevents daily routine activity	Emergency room visit or hospitalization for severe fatigue
Chills	Does not interfere with activity	Some interference with activity	Prevents daily routine activity	Emergency room visit or hospitalization for severe chills
New or worsened muscle pain	Does not interfere with activity	Some interference with activity	Prevents daily routine activity	Emergency room visit or hospitalization for severe new or worsened muscle pain

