8.3.4.4. Fever

In order to record information on fever, a thermometer will be given to participants with instructions on how to measure oral temperature at home. Temperature will be collected in the reactogenicity e-diary in the evening daily during the reactogenicity e-diary reporting period. It will also be collected at any time during the reactogenicity e-diary data collection periods when fever is suspected. Fever is defined as an oral temperature $\geq 38.0^{\circ}\text{C}$ ($\geq 100.4^{\circ}\text{F}$). The highest temperature for each day will be recorded in the reactogenicity e-diary. Temperature will be measured and recorded to 1 decimal place. Temperatures recorded in degrees Fahrenheit will be programmatically converted to degrees Celsius and then categorized according to the scale shown in [Table 3](#) during analysis.

If a fever of $\geq 39.0^{\circ}\text{C}$ ($\geq 102.1^{\circ}\text{F}$) is reported in the reactogenicity e-diary, a telephone contact should occur to ascertain further details and determine whether a site visit is clinically indicated. Only an investigator or medically qualified person is able to confirm a participant's fever as $>40.0^{\circ}\text{C}$ ($>104.0^{\circ}\text{F}$). If a participant experiences a confirmed fever $>40.0^{\circ}\text{C}$ ($>104.0^{\circ}\text{F}$), the investigator must immediately notify the sponsor and, if it is determined to be related to the administration of the study intervention, further vaccinations (if applicable) will be discontinued in that participant.

Table 3. Scale for Fever

$\geq 38.0\text{-}38.4^{\circ}\text{C}$ ($100.4\text{-}101.1^{\circ}\text{F}$)
$>38.4\text{-}38.9^{\circ}\text{C}$ ($101.2\text{-}102.0^{\circ}\text{F}$)
$>38.9\text{-}40.0^{\circ}\text{C}$ ($102.1\text{-}104.0^{\circ}\text{F}$)
$>40.0^{\circ}\text{C}$ ($>104.0^{\circ}\text{F}$)

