10.11.10.7.4. Unscheduled Visit for a Grade 3 or Suspected Grade 4 Reaction

If a Grade 3 local reaction ([Section 8.3.4.2](#)), systemic event ([Section 8.3.4.3](#)), or fever of $\geq 39.0^{\circ}\text{C}$ ($\geq 102.1^{\circ}\text{F}$) ([Section 8.3.4.4](#)) is reported in the reactogenicity e-diary, a telephone contact should occur to ascertain further details and determine whether a site visit is clinically indicated. If a suspected Grade 4 local reaction ([Section 8.3.4.2](#)), systemic event ([Section 8.3.4.3](#)), or fever ([Section 8.3.4.4](#)) is reported in the reactogenicity e-diary, a telephone contact or site visit should occur to confirm whether the event meets Grade 4 criteria.

A site visit must be scheduled as soon as possible to assess the participant unless any of the following is true:

- The participant is unable to attend the unscheduled visit.
- The local reaction/systemic event is no longer present at the time of the telephone contact.
- The participant recorded an incorrect value in the reactogenicity e-diary (confirmation of a reactogenicity e-diary data entry error).
- The PI or authorized designee determined it was not needed.

This telephone contact will be recorded in the participant's source documentation and the CRF.

If the participant is unable to attend the unscheduled visit, or the PI or authorized designee determined it was not needed, any ongoing local reactions/systemic events must be assessed at the next study visit.

During the unscheduled visit, the reactions should be assessed by the investigator or a medically qualified member of the study staff, such as a study physician or a study nurse, as applicable to the investigator's local practice, who will:

- Measure body temperature ($^{\circ}\text{F}/^{\circ}\text{C}$).
- Measure minimum and maximum diameters of redness (if present).
- Measure minimum and maximum diameters of swelling (if present).
- Assess injection site pain (if present) in accordance with the grades provided in [Section 8.3.4.2](#).

- Assess systemic events (if present) in accordance with the grades provided in [Section 8.3.4.3](#).
- Assess other findings associated with the reaction and record this on the AE page of the CRF if appropriate.
- The investigator or an authorized designee will complete the unscheduled visit assessment page of the CRF.

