3.1.2.2. Systemic Events Within 7 Days After Vaccination

Systemic events, including fever, fatigue/tiredness, headache, chills, vomiting, diarrhea, new or worsened muscle pain, and new or worsened joint pain, are reported from Day 1 through Day 7 after vaccination, where Day 1 is the day of vaccination with any study intervention. The derivations for the systemic events as described below will be handled similarly to the way that local reactions are handled for the presence for each participant, severity level, duration, onset day, and presence of severe systemic event on each and any day.

1. Presence (yes or no) of each systemic event on any day (Day 1 through Day 7) after vaccination.
2. Presence (yes or no) of any systemic event on any day (Day 1 through Day 7) after vaccination.
3. Maximum severity of each systemic event on any day (Day 1 through Day 7) after vaccination.
4. Maximum severity of any systemic event on any day (Day 1 through Day 7) after vaccination.
5. Duration of each systemic event after vaccination.
6. Onset day of each systemic event after vaccination.

The grading scale for systemic events is provided in the protocol. However, the derivation of severity of each systemic event on each day should be based on the maximum severity reported from the e-diary or AE CRF, if data are reported from both sources; or the e-diary alone if not reported from the AE CRF.

Fever is defined as a temperature of $\geq 100.4^{\circ}\text{F}$ ($\geq 38.0^{\circ}\text{C}$). The highest temperature for each day will be recorded in the e-diary. Any measure with degrees Fahrenheit will be converted to degrees Celsius for analysis. For reporting purposes, fever will be analyzed using the following temperature ranges:

- Mild (≥ 38.0 to 38.4°C from the e-diary or mild grade from the AE CRF);
- Moderate (>38.4 to 38.9°C from the e-diary or moderate grade from the AE CRF);
- Severe (>38.9 to 40.0°C from the e-diary or severe grade from the AE CRF);
- Grade 4 ($>40.0^{\circ}\text{C}$ from the e-diary or severe grade from the AE CRF, and documented $>40.0^{\circ}\text{C}$ via CRF query or other sources).

Any temperature that is confirmed as incorrect will use the correct temperature for analysis and those for which the correct temperature is unknown will not be included in the analysis.

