5.3.1.1. Reactogenicity Data

For derived variables based on the reactogenicity data, if any day of the 7-day e-diary is available, the “any day (Days 1-7)” data will be considered nonmissing.

The reactogenicity data are mostly collected through the e-diary, which does not allow participants to skip the question. Therefore, for a specific day, if the e-diary data are transferred for that day, all of the reactogenicity data for the participant on that day are nonmissing.

In general, for any participant with all 7 days of the e-diary data missing, this participant will not be included in the analysis (ie, assuming MCAR). If only 1 to 6 days of e-diary data are transferred, it is expected that these reactogenicity events would be queried by the investigator for the missing e-diary days and entered in the AE CRF if any reactogenicity was not reported in the e-diary due to missed days. Therefore, the primary analysis will use reactogenicity recorded in the AE CRF to impute the partially missed e-diary data to estimate the reactogenicity rate during the e-diary collection period. The AE CRF is designed as a log page, which means only events that occurred will be recorded and events that did not occur will not be recorded. Therefore, all remaining missing days are considered as “no.” This imputation can reasonably estimate the reactogenicity event rates during the e-diary collection period. However, data for the missing day(s) will not be imputed in the analysis of each specific day.

A sensitivity analysis will be planned for participants who completed the e-diary. Only participants with all 7 days of e-diary transferred data will be included in this sensitivity analysis.

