6.1.3.1. Main Analysis

- Estimand strategy: Treatment policy ([Section 2.2.1.3.1](#)).
- Analysis set: Reactogenicity safety population (only participants with at least 1-day e-diary data transferred are included in the calculation) ([Section 5.3.1.1](#)).
- Analysis methodology: 95% CI of the proportion of participants reporting each event will be calculated using the Clopper-Pearson method ([Section 5.2.1](#)).
- Analysis timing: Final analysis of immunogenicity objective.
- Intercurrent events and missing data: All data collected are included; partially missing e-diary data are imputed as “no” ([Section 5.3.1.1](#)); e-diary data that are confirmed as errors will not be used for analysis.
- Descriptive statistics, including the proportion (%), the numerator (n) and the denominator (N) used in the proportion calculation, and the 95% CI for percentage using the Clopper-Pearson method, will be presented for each group ([Section 5.2.1](#)).
- Bar charts with the proportions of participants for each and any local reaction and each and any systemic event throughout the 7 days will be plotted for each vaccine group. The bars will be divided into severity categories to highlight the proportions of participants by maximum severity.

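### For every diary item except temperature, an entry confirmed as an error is dropped with no replacement value, so a real mild or moderate reaction mis-entered as Grade 3 can be analysed as no reaction

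*Protocol*

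**What the plan says.** **Which entries must be followed up.** Protocol 8.3.4.2 covers local reactions: "If a Grade 3 local reaction is reported in the reactogenicity e-diary, a telephone contact should occur to ascertain further details". Protocol 8.3.4.3 covers systemic events: "If a Grade 3 systemic event is reported in the reactogenicity e-diary, a telephone contact should occur to ascertain further details". Protocol 8.3.4.4 has the same rule for fever of at least 39.0 °C, which, when it "is reported in the reactogenicity e-diary, a telephone contact should occur to ascertain further details and determine whether a site visit is clinically indicated". For suspected Grade 4 events, Protocol 10.11.10.7.4 adds that "a telephone contact or site visit should occur to confirm whether the event meets Grade 4 criteria". Lower grades are reviewed online (Protocol 8.3.4), but no contact is required.

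**What the contact can find.** Protocol 10.11.10.7.4 lists reasons why a site visit need not follow. One is "The participant recorded an incorrect value in the reactogenicity e-diary".

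**What the analysis does with it.** SAP 6.1.3.1: "e-diary data that are confirmed as errors will not be used for analysis". The same list entry fills gaps in a partly completed diary with a no. SAP 5.3.1.1 first uses reactogenicity from the AE CRF for missed days, then says "Therefore, all remaining missing days are considered as" no. SAP Table 2 and SAP 3.1.2.1.2 give No, or severity 0, to any mix of no and missing over the seven days. SAP 3.1.2.2 handles systemic events in the same way.

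**The exception.** For temperature, SAP 3.1.2.2 says "Any temperature that is confirmed as incorrect will use the correct temperature for analysis". A temperature is left out only when the correct value is unknown. No other diary item has such a rule.

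**The concern.** A participant who presses severe and tells the site on the telephone that the pain was moderate has still reported a reaction. The correct analysis value is moderate. The SAP removes the severe entry but, outside temperature, does not say that moderate goes in its place. If the item then counts as missing, the seven-day derivation can return no reaction at all.

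Local reactions and systemic events, by any and by maximum severity, are part of the primary safety analysis (Protocol 10.11.11.3.2). The rule would lower the mild, moderate and any-severity rates. Neither sensitivity analysis in SAP 6.1.3.3 is written to show how many entries were removed or what difference that made.

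**Working it through.** The plan states no figure that depends on this rule: no error rate, no expected reaction rate and no power for reactogenicity. The check is therefore a trace of the rules on example diaries, followed by the scale of one participant.

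**Inputs.** Derivation rules from SAP Table 2, 3.1.2.1.2, 5.3.1.1 and 6.1.3.1; merging of e-diary and AE CRF at the higher grade from SAP 3.1.2; about 150 enrolled per group from Protocol 10.11.11.5. Assumption: a dropped entry is treated as missing. The SAP does not say this outright. It says only that all items on a transferred day are nonmissing, which does not cover an item removed later.

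**Rule applied.** Maximum severity is the highest nonmissing grade over Days 1 to 7, and is missing only if all seven days are missing.

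| Case (non-fever item unless stated) | Result under the SAP |
|---|---|
| (a) True mild on Day 2 only, entered as Grade 3, confirmed as error, nothing in AE CRF: 0, missing, 0, 0, 0, 0, 0 | 0: the reaction is lost |
| (b) As (a), but a mild entry also on Day 3 | 1: kept |
| (c) As (a), but AE CRF records mild for Day 2 | 1: kept |
| (d) The dropped entry is the only diary datum | Missing |
| (e) True severe entered as mild, no required contact | 1, unless AE CRF records severe |
| (f) Fever: correct temperature known | Correct lower grade kept |

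In case (a), the three possible treatments of the entry compare as follows.

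- As transmitted: grade 3; severe yes; any reaction yes.
- SAP as written: grade 0; severe no; any reaction no.
- Temperature rule extended to the item: grade 1; severe no; any reaction yes.

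The last two agree on the severe count. They differ on the mild count and on any severity. That difference is the defect.

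**Scale.** One participant is 1/150 = 0.67 percentage points. If k participants in a group are in case (a), the any-severity rate for that item falls by k × 0.67: 0.67 for one, 1.33 for two, 2.00 for three. The mild and moderate rates together fall by the same amount. The composite for any local reaction (SAP Table 3) falls only if the participant's other local reactions are also negative. The number k is not given, so the actual bias cannot be computed.

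**The case against.** The strongest reply is that the SAP never says a confirmed error becomes a no. Its no rule is written for days that were not transferred, and the AE CRF is consulted before that rule applies. This stands as far as it goes: the outcome in case (a) is a reading of several sections together, and cases (b) to (d) show that it needs specific conditions. It does not close the gap. The site query in SAP 5.3.1.1 is for missed diary days, and a day with a transmitted but wrong entry was not missed. Protocol 8.3.4 says that diary data need not be entered as AEs. The query-response provision in SAP 3.1.2 covers redness, swelling and fever, in the setting of missing entries. A corrected grade for pain or headache may be on file with no stated route into the analysis.

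A reader might draw four stronger conclusions that the documents do not support.

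- *The rule biases the severe rate downward*, for example from 3/150 (2.0%, 95% CI 0.4 to 5.7) to 2/150 (1.3%, 0.2 to 4.7). If the Grade 3 entry really was an error, removing it gives the right severe count.
- *Under-recorded severe reactions are never checked, so correction can only go down.* Protocol 10.11.10.7.1 tells participants to contact the site at once about severe reactions on Days 1 to 7, whatever they entered. The higher of the diary and AE CRF grades is used, so severity can also be raised.
- *Both sensitivity analyses use the cleaned data.* SAP 6.1.3.3 is silent; the error rule appears only under the main analysis.
- *The groups are treated differently.* The staff who evaluate safety are blinded (Protocol 10.11.8.2.2), and nothing suggests this.

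**Conclusion.** The point holds in a limited form. For redness, swelling, pain and the non-fever systemic events, the SAP removes confirmed errors without substituting the verified value, although it does substitute for temperature. Read with the derivation rules, this can turn a real mild or moderate reaction into none. The effect is up to 0.67 percentage points per affected participant at 150 per group, on the mild or moderate rate and on the any-severity rate for the item.

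This rests on three conditions: the dropped item is treated as missing, no other day is positive for that item, and the AE CRF has no record of it. The frequency is unknown and may be small.

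The severe rate is at risk only if a true Grade 3 entry is wrongly confirmed as an error. That risk exists because the required contact is triggered only by Grade 3, suspected Grade 4 or fever of at least 39.0 °C, so it examines only high entries. The documents give no basis for saying that this happens.

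**What to change.** 1. **SAP 6.1.3.1.** Extend the temperature rule to every reactogenicity item: replace a confirmed error with the verified grade or size documented in the CRF at the telephone contact or unscheduled visit, and name that source.
2. **SAP Table 2 and 3.1.2.1.2**, carried to Table 3 and to systemic events through 3.1.2.2. If the correct value is unknown, treat the item-day as missing, and amend these rules so that the participant is not derived as No or 0 on that basis alone. Without this amendment the any-day result would not change, because no plus missing would still give No.
3. **SAP 6.1.3.3.** State that the diary-only sensitivity analysis uses values as transmitted, before any error removal. Report by group the number of Grade 3 entries removed or changed.

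The rules on when sites contact participants need not change. The cost is SAP wording, limited programming and a rerun of one existing table. The contact is already recorded in the CRF, but the documents do not say whether that record has a field for the corrected grade, so this needs checking. The downside is that the as-transmitted rates will include a few genuine entry errors.

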8.3.4.3. Systemic Events

During the reactogenicity e-diary reporting period, participants will be asked to assess vomiting, diarrhea, headache, fatigue, chills, new or worsened muscle pain, and new or worsened joint pain and to record the symptoms in the reactogenicity e-diary. The symptoms will be assessed by the participant as absent, mild, moderate, or severe according to the grading scale in [Table 2](#).

If a systemic event persists beyond the end of the reactogenicity e-diary period following vaccination, the participant will be requested to report that information. The investigator will enter this additional information in the CRF.

If a Grade 3 systemic event is reported in the reactogenicity e-diary, a telephone contact should occur to ascertain further details and determine whether a site visit is clinically indicated. Only an investigator or medically qualified person is able to classify a participant's systemic event as Grade 4. If a participant experiences a confirmed Grade 4 systemic event, the investigator must immediately notify the sponsor and, if it is determined

to be related to the administration of the study intervention, further vaccinations will be discontinued in that participant.

Table 2. Systemic Event Grading Scale

	Mild (Grade 1)	Moderate (Grade 2)	Severe (Grade 3)	Potentially Life-Threatening (Grade 4)
Vomiting	1-2 times in 24 hours	>2 times in 24 hours	Requires IV hydration	Emergency room visit or hospitalization for hypotensive shock
Diarrhea	2 to 3 loose stools in 24 hours	4 to 5 loose stools in 24 hours	6 or more loose stools in 24 hours	Emergency room visit or hospitalization for severe diarrhea
Headache	Does not interfere with activity	Some interference with activity	Prevents daily routine activity	Emergency room visit or hospitalization for severe headache
Fatigue/tiredness	Does not interfere with activity	Some interference with activity	Prevents daily routine activity	Emergency room visit or hospitalization for severe fatigue
Chills	Does not interfere with activity	Some interference with activity	Prevents daily routine activity	Emergency room visit or hospitalization for severe chills
New or worsened muscle pain	Does not interfere with activity	Some interference with activity	Prevents daily routine activity	Emergency room visit or hospitalization for severe new or worsened muscle pain
New or worsened joint pain	Does not interfere with activity	Some interference with activity	Prevents daily routine activity	Emergency room visit or hospitalization for severe new or worsened joint pain

